### **5.5.6 Rescue medication**

Rescue medication is defined as any new therapeutic intervention or a significant change to ongoing therapy made because a patient is experiencing either no benefit from participation in the trial or worsening/exacerbation of their disease. Rescue medication must not be used before completion of Week 16 assessments. Although no patient will be restricted from receiving necessary rescue medications for lack of benefit or worsening of disease, if rescue with prohibited biologics (as described in [Section 5.5.8](#)) occurs, patients will be discontinued from the study. Efficacy will be assessed in detail at every study visit, and patients who are deemed not to be benefiting from the study treatment based on safety and efficacy assessments (see [Section 5.5.9](#)) or for any reason on their own accord will be free to discontinue participation in the study at any time. Changes in NSAID concomitant therapy are permitted as per investigator's clinical judgment after all Week 16 assessments are completed. Please see [Section 5.5.7](#), [Section 5.5.8](#) and [Section 5.5.9](#) for further details.

Any use of rescue medication must be recorded in the Prior/Concomitant medications eCRF page.

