### **Non-steroidal anti-inflammatory drugs (NSAIDs) (including COX-1 or COX-2 inhibitors) and acetaminophen/paracetamol**

Patients on regular use of NSAIDs or paracetamol/acetaminophen should be on stable dose for at least 2 weeks before baseline to allow inclusion in the study.

NSAIDs, low strength opioids or paracetamol/acetaminophen PRN can be taken during the study; however, patients should refrain from any intake during at least the 24 hours before a visit with disease activity assessment.

After the Week 16 assessments are completed, a change in the NSAID intake regimen is permitted.

Any change of the NSAID/paracetamol/acetaminophen treatment during the trial should be recorded on the corresponding eCRF page

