## **6 Visit schedule and assessments**

Table 6-1 lists all of the assessments and indicates with an "x" when the visits are performed.

Patients should be seen for all visits on the designated day or as close to it as possible.

At a minimum, patients will be contacted for safety evaluations during the 30 days following the last study visit. Documentation of attempts to contact the patient should be recorded in the source documentation

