2.1.2 Analysis visit windows

Analysis visit windows will be used for the data that is summarized by visit; they are based on the study evaluation schedule and comprise a set of days around the nominal visit day. For any assessment, there are the protocol defined scheduled visits around which visit windows will be created to cover the complete range of days within the study. These visit windows apply to measurements taken at every visit. For assessments collected less often different visit windows will be applied as detailed below.

The analysis visit windows depend on the visit schedule for the assessments and are shown in [Table 2-1](#).

The analysis visit will be used for listing of visit and period.

The mapping described above applies to all visits (not just scheduled visits). Repeat and/or unscheduled visits (which will be numbered in the database according to new NCDS standards) will be mapped for analysis purposes in the same way as scheduled visits. This leaves the possibility, then, for multiple measurements within an analysis window. The conventions in [Table 2-2](#) will be used to determine the appropriate measurement to be summarized in the event of multiple measurements within a visit window.

Table 2-1 Analysis visit windows

Analysis Visit	Week	Scheduled Day	Variables assessed everyVisit		weight, ECG	Vital signs, LAB	PK	Visit window (Day)		Lipids	Cardiovascular panel
			ASQoL, SF-36	Immunogenicity							
Baseline		BSL	1	to 1	to 1	to 1	to 1	to 1	to 1	to 1	to 1
Week 1	1	8	2-11		2-11						
Week 2	2	15	12-18		12-18						
Week 3	3	22	19-25		19-25						
Week 4	4	29	26-43		26-43	2-71	2-43				
Week 8	8	57	44-71		44-71		44-71			2-85	
Week 12	12	85	72-99		72-99		72-99				
Week 16	16	113	100-127	2-239	100-127	72-141	100-141	2-141		86-239	2-141
Week 20	20	141	128-155		128-155						
Week 24	24	169	156-183		156-183	142-267	142-267	142-267			142-267
Week 28	28	197	184-211		184-239						
Week 32	32	225	212-239								
Week 36	36	253	240-267								
Week 40	40	281	268-295		240-323						
Week 44	44	309	296-323								
Week 48	48	337	324-351								
Week 52	52	365	352-393	240-393	324-393	268-393	268-393	268-393		240-393	268-393
Week 60	60	421	394-449	CRF visit	CRF visit	394-449	394-449	394-449		-	-

Variables assessed every visit: Patient's global assessment of disease activity (VAS), Patient's assessment of back pain intensity (VAS), BASFI, BASDAI, Spinal mobility (BASMI Linear + chest expansion), [REDACTED], hsCRP

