Note that safety assessments in Week F60 in the post treatment follow-up period will NOT be mapped to Week 1 – Week 52 of Analysis Visits

Table 2-2 Rules for flagging variables

Timing of measurement	Type of data	Rule
Baseline	All data	The last measurement made prior to administration of the first dose of study treatment. Baseline assessments scheduled for and captured on day 1 will be considered baseline measurements regardless of the time of assessment. In case several measurements are taken on day 1 after the first dose of study treatment, the first one will be used.
Post-baseline efficacy	All data	The measurement closest to the target will be used. In the event two measurements are taken equally apart (e.g. 1 before target date and 1 after) the first one will be used.
Post-baseline safety	Summary visit information (e.g. lab, ECG, etc.)	
Post-baseline safety	Notable abnormalities (e.g. lab)	The most extreme measurement in the window will be used. Note this means a patient can have a notably high and notably low measurement within a window.

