2.5 Analysis of the primary objective

2.5.1 Primary endpoint

The primary efficacy variable is the proportion of patients who achieve an ASAS 20 at Week 16. The analysis of the efficacy variable will be based on the FAS.

The ASAS response measures consist of the following assessment domains ([Sieper, 2009](#)):

Main ASAS domains:

1. Patient’s global assessment of disease activity measured on a VAS scale
2. Patient’s assessment of back pain, represented by either total or nocturnal pain scores, both measured on a VAS scale. For ASAS response analyses, the total back pain will be used.
3. Function represented by BASFI average of 10 questions regarding ability to perform specific tasks as measured by VAS scale

4. Inflammation represented by mean duration and severity of morning stiffness, represented by the average of the last 2 questions on the 6-question BASDAI as measured by VAS scale

Additional assessment domains:

5. Spinal mobility represented by the BASMI lateral spinal flexion assessment
6. C-reactive protein (acute phase reactant)

The ASAS Response Criteria (ASAS 20) is defined as an improvement of $\geq 20\%$ and ≥ 1 unit on a scale of 10 in at least three of the four main domains and no worsening of $\geq 20\%$ and ≥ 1 unit on a scale of 10 in the remaining domain.

The ASAS20 response will be evaluated in subgroups based on previous use of TNF-alpha inhibitors, hsCRP value (≤ 10 mg/L, > 10 mg/L, and ≤ 5 mg/L, > 5 mg/L) at baseline, age (< 65 yr, ≥ 65 yr), gender, weight (< 70 kg, $70 - 90$ kg, > 90 kg) at baseline.

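### The SAP's window rule gives the scheduled Week 16 visit no priority, so an early visit can be displaced by a later assessment made after permitted treatment changes

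*SAP*

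**What the plan says.** SAP 2.5.1 defines the endpoint: "The primary efficacy variable is the proportion of patients who achieve an ASAS 20 at Week 16". Table 2-1 gives Week 16 a target of Day 113 and, for variables collected at every visit, a window of Days 100 to 127. Its footnote places the ASAS 20 inputs in that group: "Variables assessed every visit: Patient's global assessment of disease activity (VAS), Patient's assessment of back pain intensity (VAS), BASFI, BASDAI". hsCRP is in the same group.

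SAP 2.1.2 adds that repeat and unscheduled visits "will be mapped for analysis purposes in the same way as scheduled visits", and it acknowledges that several measurements may then fall in one window. Table 2-2 settles which one counts for efficacy: "The measurement closest to the target will be used". For ties: "In the event two measurements are taken equally apart (e.g. 1 before target date and 1 after) the first one will be used".

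The protocol ties the freedom to change treatment to the visit, not to a study day. Section 5.5.6 states: "Rescue medication must not be used before completion of Week 16 assessments". The NSAID paragraph of section 5.5.7 states: "After the Week 16 assessments are completed, a change in the NSAID intake regimen is permitted". Section 5.5.7 also opens intra-articular steroids (within limits) and systemic corticosteroid reductions after Week 16. On visit timing, section 6 sets no numeric tolerance: "Patients should be seen for all visits on the designated day or as close to it as possible".

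SAP 2.5.3 assigns non-response for drop-out and for missing data. It does not mention values taken after rescue or a change of therapy.

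**The concern.** The protocol keeps the primary assessment free of other treatment by holding back rescue and NSAID changes until the Week 16 assessments are done. The SAP selects the Week 16 value by distance from a calendar day. The two boundaries differ whenever the Week 16 visit takes place before Day 113. Treatment may then change straight after the visit, and a further assessment nearer Day 113 becomes the value analysed. The uncontaminated assessment is set aside, and nothing later in the SAP detects this.

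At stake is whether the reported ASAS 20 is the protocol's Week 16 assessment in every patient. With about 30 patients and no control arm, each reclassified patient is visible in the result. The same rule selects the Week 16 BASDAI and hsCRP values. A related point is left open: the SAP does not say whether all components of one ASAS response must come from the same visit.

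**Working it through.** **Inputs.** Target Day 113, window Days 100 to 127, closest measurement used, ties to the first (SAP Tables 2-1 and 2-2). n = 30, assumed response 60%, control upper limit 38.7% (SAP section 3). Interval method: score with continuity correction (SAP 5.4.1).

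**1. When is the scheduled visit displaced?** Let the scheduled visit be on day s and a later in-window measurement on day u > s. The later one is used only if |u − 113| < |s − 113|.
- For s < 113 this means u runs from s + 1 to 225 − s.
- For s ≥ 113 every later day is further from the target, so no displacement is possible.

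| Scheduled visit | Distance from target | Later days that displace it |
|---|---|---|
| Day 100 | 13 | 101 to 125 |
| Day 106 | 7 | 107 to 119 (Day 120 ties, so the visit is kept) |
| Day 110 | 3 | 111 to 115 |
| Day 112 | 1 | 113 only |
| Day 113 or later | – | none |

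Days 126 and 127 never displace a scheduled visit that lies in the window.

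**2. Count of day pairs.** The window contains 27 + 26 + … + 0 = 378 pairs (scheduled day, later day). Those that displace number 25 + 23 + … + 1 = 169, all with the scheduled visit on Days 100 to 112. 169/378 = 45%. This counts day combinations; it is not a probability, because visits should cluster near Day 113. With scheduled-visit priority the count is 0 of 378.

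**3. Can a treatment change fall in between?** Yes. Rescue and NSAID changes open when the Week 16 assessments are completed, so from day s onward. For intra-articular steroids and corticosteroid reductions the wording is only after Week 16, which may mean the visit or the nominal day.

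**4. Could the next planned visit do it?** Week 20 has target Day 141. To act as the displacing measurement it would have to occur by Day 125, at least 16 days early, and at that limit the Week 16 visit must have been on Day 100. In practice the route needs a repeat or unscheduled assessment.

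**5. Size.** The plan's own figure reproduces with the Wald formula: 0.60 − 1.96 × √(0.6 × 0.4/30) = 0.4247, or 42.5%. One patient is 1/30 = 3.3 points. The lower 95% limits around the planning value are:

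| Responders | Wald | Score with continuity correction |
|---|---|---|
| 17/30 | 38.9% | 37.7% |
| 18/30 | 42.5% | 40.8% |
| 19/30 | 46.1% | 43.9% |

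The documents do not say how many extra assessments to expect. If 0 to 2 patients switch (an assumption), ASAS 20 moves by 0 to 6.7 points.

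**The case against.** The strongest reply is that this is an edge case. Three things must coincide: a Week 16 visit before Day 113, an extra assessment strictly closer to Day 113, and a treatment change between the two. Protocol 6.6.1 has its questionnaires completed at the scheduled visit. The only unscheduled sample that the public text visibly provides for is for PK (Appendix 2). The efficacy rows of Table 6-1 are not in the public text, so this is not conclusive, but it does suggest few cases or none. That part stands, and it limits the likelihood. It does not remove the rule, since SAP 2.1.2 itself foresees several measurements in one window.

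A second reply concerns timing. Protocol 3.5 places the primary endpoint analysis after Week 24, and SAP 1.1 and 2.14 say that the Week 24 analysis has been done. Changing the primary derivation afterwards needs care. That also stands, and it shapes the fix.

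A reader might infer three stronger things that the documents do not support.
- **The rule favours the drug.** Added therapy would tend to raise response. But a patient who returns because of worsening may score worse, and a permitted corticosteroid reduction could lower response. Rescue with a prohibited biologic leads to study discontinuation, and drop-outs count as non-responders from that time.
- **Any assessment up to Day 127 can replace the visit.** The reach is Day 125 at most, and shorter the nearer the visit lies to Day 113.
- **Components are chosen one by one from different days.** The SAP does not say so. Selection by component and selection by visit are both possible readings.

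**Conclusion.** The point holds as a minor one. On the text, a scheduled Week 16 assessment made on Days 100 to 112 can be replaced by a later one taken after a permitted treatment change, and neither the window rules nor the missing-data rules prevent it. A visit on or after Day 113 is safe from later measurements.

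Each patient whose response switches moves ASAS 20 by 3.3 points. The frequency is unknown and probably low, and the direction is not established. At the planning value, one responder fewer takes the lower limit by the SAP's interval method from 40.8% to 37.7%, across the 38.7% control limit cited in section 3. A reader might infer that the study's conclusion could turn on this rule. The documents do not support that: SAP 2.5.2 defines no hypothesis, the comparison appears only as sample-size context, and no affected patient has been shown. The conclusion rests on reading Table 2-2 literally and on the absence of any scheduled-visit priority elsewhere in the public text.

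**What to change.** In SAP Table 2-2, for post-baseline efficacy at Week 16:
1. Use the scheduled Week 16 visit when it lies in the window.
2. Use a repeat or unscheduled measurement only if the scheduled one is missing from the window and the measurement precedes any recorded rescue, NSAID change, corticosteroid change or intra-articular steroid. If no measurement qualifies, SAP 2.5.3 already gives non-response for binary variables, and continuous variables stay missing.
3. Take all components of an ASAS response from one visit.

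Because the Week 24 analysis is done, first list every patient whose flagged Week 16 record is not the scheduled visit. If there are none, a statement to that effect shows that no scheduled value was displaced. If there are some, report ASAS 20 under both rules and document the change in SAP section 4, which now records no change.

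The cost is a few sentences, a small programming change and one listing. Data collection and treatment rules are untouched. The downside is that some values may lie a few days further from Day 113.

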2.2 Analysis sets

The following analysis sets will be used in this study:

Full analysis set (FAS): The FAS will be comprised of all patients who entered into the treatment periods.

Safety set: The safety set includes all patients who took at least one dose of study treatment during the treatment periods.

Note that patients not exposed to study drug at any visit (DVSPID = TRT01) will be excluded from the Safety set.

2.2.1 Subgroup of interest

[Table 2-3](#) displays the subgroup of interest and endpoints evaluated based on the subgroups.

Table 2-3 Subgroup of interest and endpoints evaluated

Subgroup of interest	Endpoints

• Previous use of TNF-alpha inhibitors	
• Primary and all secondary endpoints• Crude incidence of AE, SAE by SOC and PT

• hsCRP value (≤ 10 mg/L, >10 mg/L) at baseline	
• Primary and all secondary endpoints

• hsCRP value (≤ 5 mg/L, > 5 mg/L) at baseline	
• Primary and selected secondary endpoint (ie, ASAS20 and ASAS 40)

• Age (< 65 yr, ≥ 65 yr)• Gender• Weight (< 70 kg, $70 - 90$ kg, > 90 kg)	
• Primary and selected secondary endpoint (ie, ASAS20 and ASAS 40)• Crude incidence of AE, SAE by SOC and PT

Note that the threshold value for subgroup analysis of hsCRP (≤ 10 mg/L, >10 mg/L), age, and weight is same as the one in CTD Clinical Overview of Secukinumab in Ankylosing Spondylitis in EU and US.

2.3 Patient disposition, demographics and other baseline characteristics

2.3.1 Patient disposition

The number of patients who entered the screening period will be presented. In addition, the reasons for screen failures will be provided.

The number and percentage of patients in the safety set who completed treatment periods, and Post-treatment follow-up, and who discontinued the study prematurely (including the reason for discontinuation) will be presented.

For each protocol deviation (PD), the number and percentage of patients for whom the PD applies will be tabulated for entire period (i.e., all PDs will be presented.) in the safety set.

2.3.2 Demographics and other baseline characteristics

The following common background and demographic variables will be summarized:

Continuous variables:

- Age at the time of informed consent
- Height
- Weight
- Body mass index (BMI) = (body weight in kilograms) / (height in meters)²

For BMI, height and body weight of the last value prior to baseline is used. If there is no weight recorded prior to taking of study drug, BMI will be missing.

Categorical variables:

- Age categories (<65 years, 65 years and older, 75 years and older)
- Gender
- Race
- Ethnicity
- Smoking status at baseline

Baseline disease characteristics will also be summarized for the following variables:

Patient's global assessment of disease activity and other ASAS components, hsCRP, [REDACTED], TNF alpha inhibitor inadequate responder, number and previous use (yes/no) of TNF-alpha inhibitor, use (yes/no) and separate dose of methotrexate (mg/week), sulfasalazine (g/day) and systemic corticosteroids (mg/day) at baseline, time since first diagnosis of AS (years), time since onset of inflammatory back pain (years), HLA-B27, [REDACTED], BASDAI (Total and #2), BASMI (linear), BASMI components (all seven in original units).

Calculation method for dose of systemic corticosteroids is described in 2.4.2.

Unless otherwise specified, summary statistics will be presented for continuous variables and for all patients (total) in the safety set. The number and percentage of patients in each category will be presented for categorical variables for all patients (total) in the safety set.

2.3.3 Medical history

Any condition entered on the Relevant medical history / current medical conditions CRF will be coded using the MedDRA dictionary. They will be summarized by system organ class (SOC) and preferred term (PT) of the MedDRA dictionary. Summaries for cardiovascular medical history and ankylosing spondylitis medical history will also be provided on the safety set.

Smoking history will be summarized on the safety set.

2.4 Treatments (study treatment, rescue medication, concomitant therapies, compliance)

2.4.1 Study treatment / compliance

The analysis of study treatment data will be based on the safety set. The number of injections will be summarized. The duration of exposure to study treatment will also be summarized. In addition, the number and percentage of patients with cumulative exposure levels (e.g., any exposure, \geq 1 week, \geq 2 weeks, \geq 3 weeks, \geq 4 weeks, \geq 8 weeks, etc.) will be presented.

In general, duration of exposure is defined as the time from first dose of study treatment to the end of treatment period. The end of treatment period will be defined as the last dose plus 84 days or last visit (including Week F60 in the Post-treatment follow-up period), whichever occurs earlier, i.e., for patients who discontinued or have their last visit earlier than last dose plus 84 days, the end of study treatment exposure will be the date of the last study visit.

Duration of exposure (days) = (last visit date or last dose date + 84 days whichever comes earlier) – first dose date + 1

Duration of exposure (years) = duration of exposure (days) / 365.25

2.4.2 Prior and concomitant therapies

Prior and concomitant medications will be summarized in separate tables based on the safety set. Prior medications are defined as treatments taken and stopped prior to first dose of study treatment. Any medication given at least once between the day of first dose of study treatment and within 84 days after last dose will be a concomitant medication, including those which were started pre-baseline and continued into the treatment periods.

Medications will be presented in alphabetical order, by Anatomical Therapeutic Classification (ATC) codes and grouped by anatomical main group. Tables will show the overall number and percentage of patients receiving at least one treatment of a particular ATC code and at least one treatment in a particular anatomical main group.

Prior surgeries and procedures are defined as surgeries and procedures done prior to first dose of study treatment. Any surgeries and procedures done between the day of first dose of study

treatment and within 84 days after last dose will be concomitant surgeries and procedures, including those which were started pre-baseline and continued into the period where study treatment is administered.

Significant prior and concomitant non-drug therapies and procedures will be summarized by primary system organ class and MedDRA preferred term on the safety set.

The number and percentage of patients receiving prior and concomitant ankylosing spondylitis therapy (disease-specific therapy) will be presented by category for medication preferred term on the safety set. The category is “Topical glucocorticoids”, “Systemic glucocorticoids”, “Nonsteroidal anti-inflammatory drugs”, “Tumour necrosis factor alpha inhibitor”, and “Other ankylosing spondylitis medication”. Glucocorticoids in the eCRF page will be divided into two; Topical one and Systemic one based on whether the Route (CMROUTE in SDTM) is Topical or not. The category for NSAIDs will be specified based on whether the data is from the NSAIDs CRF page or not.

At a minimum, methotrexate, sulfasalazine and systemic corticosteroid intake at baseline (Day 1) will be presented based on the amount taken per time unit, e.g. mg/day. Since different steroids have different strengths the following multiplication factors will be used to convert a dose in mg into a prednisone equivalent dose in mg:

Cortisone (0.20), hydrocortisone (0.25), prednisolone (1.0), triamcinolone (1.25), methylprednisolone (1.25), dexamethasone (6.67), betamethasone (8.33) ([corticosteroid converter website](#)).

The reported dose and frequency of intake will be converted into the desired units. If the frequency is missing or specified as ‘per needed’, ‘unknown’, ‘once’, ‘other’ or if the dose or dose unit is missing, then the medication will not be part of the presentation.

